10. DATA COLLECTION, SITE MONITORING, AND ADVERSE EXPERIENCE REPORTING

10.1. Records to Be Kept

All signed informed consent forms will be maintained in a locked filing cabinet accessible only to the [name], Clinical Director, and research coordinator.

This cabinet is located in a limited-access room which requires an authorized badge to enter.

All records collected for research-only purposes (research EEG, metabolic assays) will be maintained in a secure fashion. Paper records will be maintained in a locked filing cabinet in a limited-access room. Electronic records will be maintained on an internal, secure UTSW server accessible only by authorized username and password. These servers are backed up nightly, are HIPAA and HiTECH compliant, and are behind the same level of security as UT Southwest and Children's Medical Center Dallas' medical records.

Subject's will be assigned a study ID, and all materials collected for research purposes will be de-identified using this study ID, including data and case report forms. A file containing the link will be maintained for the duration of active study procedures and during data cleaning. Once the data has been cleaned, the file containing the link to patient ID will be deleted and destroyed.

Records collected for clinical and research purposes (e.g., blood tests and EEGs completed at Children's Medical Center) will become part of the subject's medical record at Children's Medical Center and may be copied and transferred to the subject's primary referring physician at the patient request.

The investigator-sponsor will maintain records in accordance with Good Clinical Practice guidelines; to include:

- FDA correspondence related to the IND application and Investigational Plan; including copies of submitted Form FDA 3500 A, supplemental IND applications, current investigator lists, progress reports, and failure to obtain informed consent reports;
- IRB correspondence (including approval notifications) related to the clinical protocol; including copies of adverse event reports and annual or interim reports;
- Current and past versions of the IRB-approved clinical protocol and corresponding IRB-approved consent form(s) and, if applicable, subject recruitment advertisements.
- Signed Investigator's Agreements and Certifications of Financial Interests of Clinical Investigators;
- Curriculum vitae (investigator-sponsor and clinical protocol sub-investigators);
- Certificates of required training (e.g., human subject protections, Good Clinical Practice, etc.) for investigator-sponsor and listed sub-investigators;
- Normal value(s)/range(s) for medical/laboratory/technical procedures or tests included in the clinical protocol;
- Laboratory certification information;
- Instructions for on-site preparation and handling of the investigational study treatment (i.e., if not addressed in the clinical protocol);
- Signed informed consent forms;

- Completed Case Report Forms; signed and dated by investigator-sponsor;
- Source Documents or certified copies of Source Documents;
- Monitoring visit reports;
- Copies of investigator-sponsor correspondence to sub-investigators, including notifications of adverse effect information;
- Subject screening and enrollment logs;
- Subject identification code list;
- Investigational drug accountability records, including documentation of disposal;
- Final clinical study report.

The investigator-sponsor will retain the specified records and reports for up to 2 years after the marketing application is approved for the investigational product; or, if a marketing application is not submitted or approved for the investigational drug, until 2 years after investigations under the IND have been discontinued and the FDA so notified.

10.2. Role of Data Management

This is a single site study; there are no other clinical sites or statistical center. The CTSA division at UT Southwestern Medical Center will create and maintain our database for this study.

10.3. Quality Assurance

Study personnel and physicians will be trained prior to protocol initiation. [name] will participate in several subject intake and evaluations with the physician investigators throughout the study period to ensure quality of clinical exams. In addition, [name] will review records collected during these clinical exams to ensure completeness and accuracy.

The Clinical Director will supervise training of all support personnel, including the research coordinator. She will provide monitoring of regulatory compliance on all aspects of the study, including review of research records and consent forms. The research coordinator will be responsible for submitting all IRB documentation, but will work with the Clinical Director when necessary to ensure compliance.

[name] and Clinical Director will work together to ensure all personnel are properly trained on their role in the project, and will work together on all federal submissions to remain compliant with reporting requirements.

In the event that monitoring authorities request records, [name] and the Clinical Director will work together with the authorities to provide all requested and required documentation.

10.4. Adverse Experience Reporting

Adverse experiences will be collected from subjects at each daily visit. Adverse experiences will be recorded using Adverse Event forms from the NINDS common data elements for epilepsy website (VA toxicity scale). Adverse events will be reported following all requirements set forth by the FDA, OHRP, and local IRB.

10.4.1. Adverse event definitions

Adverse effect. Any untoward medical occurrence in a clinical study of an investigational product, regardless of the causal relationship of the problem with the product.

Associated with the investigational product. There is a reasonable possibility that the adverse effect may have been caused by the investigational product.

Disability. A substantial disruption of a person's ability to conduct normal life functions.

Life-threatening adverse effect. Any adverse effect that places the subject, in the view of the investigator-sponsor, at immediate risk of death from the effect as it occurred (i.e., does not include an adverse effect that, had it actually occurred in a more severe form, might have caused death).

Serious adverse effect. Any adverse effect that results in any of the following outcomes: death, a life-threatening adverse effect, inpatient hospitalization or prolongation of existing hospitalization, a persistent or significant disability/incapacity, or a congenital anomaly/birth defect.

Hospitalization shall include any initial admission (even if less than 24 hours) to a healthcare facility as a result of a precipitating clinical adverse effect; to include transfer within the hospital to an intensive care unit. Hospitalization or prolongation of hospitalization in the absence of a precipitating, clinical adverse effect (e.g., for a preexisting condition not associated with a new adverse effect or with a worsening of the preexisting condition; admission for a protocol-specified procedure) is not, in itself, a serious adverse effect.

Unexpected adverse effect. Any adverse effect, the frequency, specificity or severity of which is not consistent with the risk information described in the clinical study protocol(s) or elsewhere in the current IND application, as amended.

Unanticipated adverse effect. Any serious adverse effect on health or safety or any life-threatening problem or death caused by, or associated with, an investigational product, if that effect, problem, or death was not previously identified in nature, severity, or degree of incidence in the investigational plan or IND application (including a supplementary plan or application), or any other unanticipated seri-

ous problem associated with an investigational product that relates to the rights, safety, or welfare of subjects.

10.4.2. Recording and assessment of adverse effects.

All observed or volunteered adverse effects (serious or non-serious) and abnormal test findings, regardless of treatment group, if applicable, or suspected causal relationship to the investigational product will be recorded in the subjects' case histories. For all adverse effects, sufficient information will be pursued and/or obtained so as to permit 1) an adequate determination of the outcome of the effect (i.e., whether the effect should be classified as a serious adverse effect) and; 2) an assessment of the causal relationship between the adverse effect and the investigational product.

Adverse effects or abnormal test findings felt to be associated with the investigational product will be followed until the effect (or its sequelae) or the abnormal test finding resolves or stabilizes at a level acceptable to the investigator-sponsor.

10.4.3 Abnormal test findings:

An abnormal test finding will be classified as an adverse effect if one or more of the following criteria are met:

- The test finding is accompanied by clinical symptoms.
- The test finding necessitates additional diagnostic evaluation(s) or medical/surgical intervention; including significant additional concomitant drug or other therapy. (Note: simply repeating a test finding, in the absence of any of the other listed criteria, does not constitute an adverse effect.)
- The test finding leads to a change in study dosing or exposure or discontinuation of subject participation in the clinical study.
- The test finding is considered an adverse effect by the investigator-sponsor.

10.4.4. Causality and severity assessment:

The investigator-sponsor will promptly review documented adverse effects and abnormal test findings to determine 1) if the abnormal test finding should be classified as an adverse effect; 2) if there is a reasonable possibility that the adverse effect was caused by the investigational product; and 3) if the adverse effect meets the criteria for a serious adverse effect.

If the investigator-sponsor's final determination of causality is "unknown and of questionable relationship to the investigational product", the adverse effect will be

classified as associated with the use of the investigational product for reporting purposes. If the investigator-sponsor's final determination of causality is "unknown but not related to the investigational product", this determination and the rationale for the determination will be documented in the respective subject's case history.

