6.2.2. On-Study/On-Intervention Evaluations

6.2.2.1. Entry Day 1

Subjects will be admitted for a 48 hour inpatient stay for oil administration and monitoring. Entry evaluations will be done within a day of pre-entry and consist of a nutritional assessment, and a blood draw to evaluate hematology and blood chemistry, including a random glucose. We will also obtain blood that is left over from the samples above (if available) or draw an additional 3 mL of blood, if needed, to measure C7 ketones. The collection of this blood for measurement of ketones is optional. A continuous EEG will be completed on subjects over the 48 hour inpatient stay. A peripheral IV will be placed to allow for immediate treatment of breakthrough seizures, should they occur.

6.2.2.2. Day 2

Subjects will be administered C7 starting on the morning of Day 2. Subjects will be given oil at a rate of 45% of their daily caloric intake, divided into 4 doses (breakfast, lunch, dinner, and before bed). A clinical assessment and a side effect assessment will be done. Subjects will be maintained on continuous EEG for the duration of C7 administration. Subjects will receive their final dose in the evening on Day 2. Subjects will have a blood draw to evaluate hematology and blood chemistry. Subjects will undergo a random glucose and beta-hydroxybutyrate level in the morning with their first dose of C7 and at bedtime with their last dose of oil. We will also obtain blood that is left over from the samples above (if available) or draw an additional 3 mL of blood, if needed, to measure C7 ketones. The collection of this blood for measurement of ketones is optional.

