7. MANAGEMENT OF ADVERSE EXPERIENCES

Previous experience with C7 oil in different populations has yielded no serious adverse effects. Due to the limited nature of the use of C7 oil, there is no data available on how frequent the following side effects occur, nor if there are differences between normal diet or ketogenic diet.

Breakthrough Seizures: There is the possibility that the administration of C7 oil may result in the subject dropping out of ketosis very quickly, which may lead to breakthrough seizures. Management of these breakthrough seizures will follow standard of care protocol, which could include IV or rectally administered anti-convulsant medications.

Diarrhea: Subjects who experience diarrhea may be instructed to increase the amount of fiber consumed with each meal. In addition, C7 will be administered in a fat free, sugar free food item, such as yogurt or pudding, and subjects are instructed to consume this food over 30 minutes in order to minimize diarrhea. Subjects who cannot tolerate the maximum tolerable dose will be discontinued from the study.

Stomach pain: Subjects who experience stomach pain at any time during the treatment will, under the direct supervision of [name] or M.D. co-investigator, be assessed for severity. If subjects cannot tolerate the recommended dose due to severe stomach pain, they will be discontinued from the study.

Weight gain: Although weight gain is a possible side effect of C7 ingestion, it is a long-term effect, and we do not anticipate significant weight gain over the course of one day.

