10.4.5. Reporting of adverse effects to the FDA

The investigator-sponsor will submit a completed Form FDA 3500 A to the FDA for any observed or volunteered adverse effect that is determined to be an unanticipated adverse effect. A copy of this completed form will be provided to all participating sub-investigators.

The completed Form FDA 3500 A will be submitted to the FDA as soon as possible and, in no event, later than 10 working days after the investigator-sponsor first receives notice of the adverse effect.

If the results of the sponsor-investigator's follow-up evaluation show that an adverse effect that was initially determined to not constitute an unanticipated adverse effect does, in fact, meet the requirements for reporting; the investigator-sponsor will submit a completed Form FDA 3500 A as soon as possible, but in no event later than 10 working days, after the determination was made.

For each submitted Form FDA 3500 A, the sponsor-investigator will identify all previously submitted reports that addressed a similar adverse effect experience and will provide an analysis of the significance of newly reported adverse effect in light of the previous, similar report(s).

Subsequent to the initial submission of a completed Form FDA 3500 A, the investigator-sponsor will submit additional information concerning the reported adverse effect as requested by the FDA.

10.4.6. Reporting of adverse effects to the responsible IRB.

In accordance with applicable policies of the University of Texas Southwestern Medical Center Institutional Review Board (IRB), the investigator-sponsor will report, to the IRB, any observed or volunteered adverse effect that is determined to meet all of the following criteria: 1) associated with the investigational product; 2) a serious adverse effect; and 3) an unexpected adverse effect. Adverse event reports will be submitted to the IRB in accordance with the respective IRB procedures.

Applicable adverse effects will be reported to the IRB as soon as possible and, in no event, later than 10 calendar days following the investigator-sponsor's receipt of the respective information. Adverse effects which are 1) associated with the investigational drug or, if applicable, other study treatment or diagnostic prod-

uct(s); 2) fatal or life-threatening; and 3) unexpected will be reported to the IRB within 24 hours of the investigator-sponsor's receipt of the respective information.

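### Section 10.4.1 has no medically-important-event criterion, so an adverse effect treated on the unit during the planned C7 admission is non-serious unless it is life-threatening, leads to intensive care, prolongs the stay or disables

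*Combined protocol and SAP*

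**What the plan says.** Section 10.4.1 defines a serious adverse effect by a closed list. It opens with "Any adverse effect that results in any of the following outcomes: death, a life-threatening adverse effect, inpatient hospitalization or prolongation of existing hospitalization" and ends with "a persistent or significant disability/incapacity, or a congenital anomaly/birth defect". Hospitalization means an initial admission caused by an adverse effect, however short, "to include transfer within the hospital to an intensive care unit". By contrast, "admission for a protocol-specified procedure) is not, in itself, a serious adverse effect". The life-threatening criterion is narrow: it "does not include an adverse effect that, had it actually occurred in a more severe form, might have caused death".

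Section 6.2.2.1 sets the location: "Subjects will be admitted for a 48 hour inpatient stay for oil administration and monitoring". Section 5.4 confirms that no C7 is given outside the hospital. An intravenous line is placed on entry so that seizures can be treated at once. Section 7 names breakthrough seizure as the first hazard of C7 and adds: "Management of these breakthrough seizures will follow standard of care protocol, which could include IV or rectally administered anti-convulsant medications".

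Section 10.4.6 sends an event to the IRB only if it is "1) associated with the investigational product; 2) a serious adverse effect; and 3) an unexpected adverse effect". Section 10.4.5 sends an event to the FDA only if it is unanticipated, as defined in 10.4.1. The opening of 10.4 separately commits the trial to the reporting requirements of the FDA, OHRP and IRB, without stating what they are.

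**The concern.** Apart from death, immediate threat to life, lasting disability and birth defect, the definition identifies a serious event by its hospital consequence. That works when subjects live at home. Here they are already inpatients whenever C7 is given, so the most common of those consequences, a new admission, cannot occur. The hazard that Section 7 lists first is one the unit is equipped to treat on the spot, and that treatment need not trigger any item on the list.

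At stake is the meaning of the trial's serious-event count. The protocol itself sums up earlier C7 experience by the absence of serious events (Sections 2.2 and 7), and Section 5.1.4 foresees updating the safety information after this trial. A count of zero from a setting that disables one of the criteria would be hard to compare with a count from a later trial in outpatients. The same classification also decides which events can become reportable.

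**Working it through.** The plan states no figure on this point, so there is none to reproduce. The check runs one event through the definitions: a breakthrough seizure on Day 2, stopped with rescue medication on the unit, with discharge at about noon on Day 3 as planned.

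**Step 1. Seriousness under 10.4.1**

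| Criterion | Can it apply during the stay? | This event |
|---|---|---|
| Death | Yes | No |
| Life-threatening | Yes, if the investigator-sponsor sees actual immediate risk of death | No, unless so judged |
| New admission | No: the subject is already admitted under the protocol | No |
| Transfer to intensive care | Yes | No |
| Prolonged stay | Yes | No |
| Lasting disability | Yes | No |
| Birth defect | Not relevant | No |

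Result: non-serious. Four non-fatal routes remain open during the stay (life threat, intensive care, prolongation, disability), but an event treated successfully on the unit takes none of them.

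**Step 2. The same event elsewhere.** If the seizure happened at home, for example between discharge on Day 3 and the Day 4 visit, and led to even a short admission, it would be serious. The classification therefore differs by location for the same clinical event.

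**Step 3. Is the idea absent from the protocol?** No. Section 10.4.3 uses the need for medical intervention as a test, but only to decide whether an abnormal test finding is an adverse effect. It is not used to decide whether an adverse effect is serious.

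**Step 4. Reporting**

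- IRB (10.4.6): associated, serious and unexpected must all hold. The event fails on serious. It may also fail on unexpected, because 10.4.1 judges that against the protocol's risk information and Section 7 already names breakthrough seizures. It could pass only if its frequency, specificity or severity went beyond that information. Section 7 says no frequency data exist.
- FDA (10.4.5): the definition of unanticipated covers serious effects, life-threatening problems, deaths and other unanticipated serious problems. A non-serious seizure would not ordinarily qualify, and the requirement that the effect was not previously identified is again a second filter.

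**Step 5. What still captures the event.** Section 10.4.2 records every adverse effect whatever its seriousness. Section 6.3.8 logs visible seizures with time and description, and continuous EEG runs throughout. Section 9.1 uses clinical seizure activity in the go/no-go rule. The log as described does not mention whether rescue was given.

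**Step 6. Size.** No rescue rate is given, so the following is illustration only.

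- Time available to settle: assuming a first dose at 08:00 on Day 2, the time to noon on Day 3 is 16 + 12 = 28 h. A first dose between 07:00 and 09:00 gives 29 to 27 h.
- Suppose 3 of 15 subjects (3/15 = 20%) are rescued on the unit and take none of the remaining routes. The serious count is 0/15. The exact upper 95% limit is 1 − 0.025^(1/15) = 1 − 0.782 = 0.218, so the interval is 0 to 21.8%. If all three would have been admitted from home, the count there would be 3/15.
- The go rule asks for unaltered findings in at least 3 of 5 subjects per age group, so it tolerates alteration in 2 × 3 = 6 of 15 (40%). If each rescued subject counts as altered and there are no more than two per group, anywhere from 0 to 6 rescued subjects is compatible with both a go and a serious count of zero.

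**The case against.** The strongest reply is that only a label is lost. The seizure is recorded, logged and seen on EEG. Section 5.3.3 has study physicians contacted as soon as possible, Section 8 stops C7 for severe seizures unusual for the subject, and 10.4.2 follows associated effects to resolution or stabilization. This is right and limits the point to classification and reporting. Four stronger readings that a reader might infer are not supported:

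- *Only a delayed discharge can make the event serious.* Section 10.4.1 also provides for intensive care transfer, life threat and disability.
- *The event goes uncounted, or the serious count drives the go/no-go decision.* Section 9.1 lists EEG, clinical seizure activity, glycemia and ketosis. The serious-event count is not among them, and a breakthrough seizure bears on the rule directly.
- *Every seizure given intravenous or rectal rescue should be serious.* That would be stricter than the at-home rule, under which rescue without admission is also non-serious. Section 5.1.3 keeps subjects on their usual rescue medication, so a habitual seizure treated in the habitual way could become serious.
- *A wider definition would by itself secure reporting.* Expectedness remains a filter, as Step 4 shows.

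It can also be said that the general clause in 10.4 brings in outside requirements that may close the gap. Their content is not in the documents, so the clause neither closes nor confirms it. Under 10.4.4 the investigator-sponsor decides seriousness, and 10.4.1 is the only definition supplied.

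**Conclusion.** The point holds as a gap in classification and reporting. The list in 10.4.1 is closed, it lacks a medically-important-event criterion, and the planned admission disables the new-admission route while C7 is being given. An adverse effect managed on the unit with on-time discharge is non-serious unless it is life-threatening, leads to intensive care or causes disability. The gap matters most for events that Section 7 does not name, because those would pass the expectedness filter and only the seriousness test keeps them from being reportable. For breakthrough seizures it mainly affects the serious-event count.

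The size cannot be estimated from the documents. The 3/15 and 28 h figures rest on an assumed rescue rate and an assumed dosing time, and the contrast with 3/15 further assumes that all three subjects would have been admitted from home. Part of the text between Sections 9.3 and 9.5, where the monitoring committee is described, was not available, so nothing is claimed about what that committee receives. This is a worthwhile and inexpensive improvement, not a flaw that undermines the trial's outcomes.

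**What to change.** Three changes, none of which alters patient care:

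1. Add to the definition of a serious adverse effect in 10.4.1 that an event during the protocol admission is also serious if, in the investigator-sponsor's judgement, it is medically important or would have led to hospital admission had the subject been at home. Do not make every intravenous or rectal rescue automatically serious. Sections 10.4.5 and 10.4.6 already use the 10.4.1 terms and would follow.
2. In Section 9.5, commit to a separate tabulation, by age group and overall, of all rescue-treated seizures during the stay, whatever their seriousness or expectedness. Add a field for rescue use to the seizure log or case report form so that the table can be filled.
3. Reconcile 10.4.1 with the general clause in 10.4, stating which definition governs if the outside requirements are wider.

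The cost is a short amendment, one data field, possibly a few more reports, and a serious-event count that may look slightly less favourable.
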